18.4.2.2 Recurrence

Recurrence is defined as Global Response at EOT but re-emergence of the baseline fungal disease during the post treatment follow-up. Re-emergence of the fungal disease is required to be with the same species and involving the same site that was initially identified at Baseline.

Recurrence will be assessed at the 25-Day FU visit (25 days after EOT, 32 days after first dose) for subjects with VVC and at the 6-Week FU (42 days after EOT) for all other subjects as a secondary efficacy endpoint. For CPA subjects, recurrence will also be assessed at Day 180.

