7.2 Rationale for the Study

This study is being conducted to evaluate the efficacy, safety and PK of ibrexafungerp in male and female subjects ≥ 18 years of age with documented severe fungal diseases for whom SOC antifungal treatment is not appropriate due to refractoriness, resistance, intolerance, relapse, toxicities, need for oral therapy or other reasons.

Eligible subjects must be selected based on study criteria and be approved for selection by the Sponsor or Sponsor designee.

Subjects must have a documented eligible fungal disease that has been refractory to, has relapsed after, or the subject has intolerance to or demonstrated toxicities resulting from an approved SOC antifungal treatment, or has an isolate resistant to, or that has a high MIC and is unlikely to respond to SOC antifungal treatment. Subjects are also eligible if, in the judgement of the Investigator, continued IV antifungal therapy is not feasible or desirable due to clinical or logistical circumstances or if other oral antifungal alternatives are not appropriate. Refractoriness, defined as persistent clinical, radiological or mycological evidence of fungal disease, and intolerance, including presence of, history of or anticipated toxicities (e.g. drug-to-drug interactions) associated with administration of SOC antifungal agents, will be determined by the Investigator.

The primary efficacy endpoint of the study is Global Response (composite assessment of clinical, radiological and mycological responses) as determined by a Data Review Committee (DRC). The primary endpoint will be determined at the TOC visit for VVC, CMC, CPA and ABPA and at the EOT visit for all other fungal diseases.^{7,8} Clinical response will be evaluated by the signs and symptoms of the infection and/or imaging scans, if applicable. Mycological response will be assessed by mycological testing (fungal culture, KOH and other fungal stains, T2 testing) and/or serological testing (including GMI, *Coccidioides* titers, and β -D-glucan levels, among others),⁹ if applicable. Recurrence will be assessed at the 25-Day FU visit (25 days after EOT) for subjects with VVC and at the 6-Week FU visit (42 days after EOT) for all other subjects as a secondary efficacy endpoint. Recurrence is defined as Global Response at EOT (TOC for VVC) but re-emergence of the baseline fungal disease (with the same fungal species and involving the same site) during the post treatment follow-up.

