Acute or chronic invasive candidiasis, including candidemia	
• Histopathologic, cytopathologic, or direct microscopic examination of a specimen obtained by needle aspiration or biopsy from a normally sterile site showing yeast cells—for example, Candida species showing pseudohyphae or true hyphaeOR• Recovery of a Candida spp. by culture of a sample obtained by a sterile procedure (including a freshly placed [<24 h ago] drain) from a normally sterile site showing a clinical or radiological abnormality consistent with an infectious disease processOR• Blood culture positive for Candida spp.OR• Alternative approved diagnostic method such as T2 testing or β-D-glucan levels (two consecutive positive test results), and at least one of the following: temperature $\geq 38^{\circ}\text{C}$ or $<36^{\circ}\text{C}$, systolic blood pressure <90 mmHg or a decrease of >30 mmHg from normal baseline, local signs or symptoms or radiologic findings of invasive candidiasis	
For acute invasive candidiasis, including candidemia refractoriness is defined as meeting one or more of the following criteria:
 
• Persistence of mycological evidence of Candida infection after >3 days of SOC antifungal therapy. Acceptable mycological evidence for this study includes:
○ Persistently positive culture from a normally sterile site○ Persistently positive T2 test○ β-D-glucan with elevated values equal to or increasing from Baseline (i.e., before start of SOC antifungal therapy)• Antifungal susceptibility results indicating that the Candida isolate is not susceptible to the SOC antifungal therapy being administered, indicating a high risk of therapeutic failure• Antifungal susceptibility results or local epidemiology indicating high risk of antifungal resistance with increased risk of therapeutic failure to SOC (e.g., Candida auris) 
For chronic disseminated candidiasis refractoriness is defined as any of the following:
 
• Persistent clinical manifestations such as debilitating fever after 12 weeks of initiating SOC antifungal treatment• Lack of changes in radiological imaging lesions >12 weeks after starting SOC antifungal treatment

Fungal Disease	Eligibility Criteria	
	Diagnostic Criteria	Refractoriness/Resistance/Intolerance ^a /Toxicity ^b /Relapse ^c Criteria

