Acute or chronic severe mucocutaneous candidiasis, including: 
• Esophageal candidiasis (EC)• Oropharyngeal candidiasis (OPC)• Chronic mucocutaneous candidiasis (CMC)• Vulvovaginal candidiasis (VVC)	
• EC: Clinical manifestations and endoscopic findings consistent with EC plus potassium hydroxide (KOH) or fungal stain from biopsy or brushing indicating yeast infection.• OPC, CMC: Evidence of clinical manifestations and mycological documentation (positive fungal stain from biopsy or positive Candida spp. culture obtained from the affected site).• VVC: Evidence of clinical manifestations with total composite signs and symptoms score of 4 or more in the vulvovaginal signs and symptoms (VSS) Scale (Section 21.4 [Appendix D]) and a positive Candida spp. culture obtained from a vaginal sample.	
For EC and OPC, refractoriness is defined as meeting the following criteria:
 
• Lack of clinical improvement or worsening of infection after receipt of SOC antifungal therapy for at least 7 consecutive days 
For CMC, refractoriness is defined as meeting the following criteria:
 
• Lack of clinical improvement or worsening of the mucocutaneous manifestations of CMC after receipt of SOC antifungal therapy for at least 21 consecutive days 
For VVC, refractoriness is defined as meeting any of the following criteria:
 
• Lack of clinical improvement or worsening of the infection after receipt of SOC antifungal therapy with documentation of persistence of Candida spp. in a vaginal sample obtained after completion of SOC antifungal therapy• Recurrent VVC caused by Candida glabrata• Recurrent VVC caused by any Candida species with a MIC for fluconazole \geq 16 μg/mL

Eligibility Criteria		
Fungal Disease	Diagnostic Criteria	Refractoriness/Resistance/Intolerance^a/Toxicity^b/Relapse^c Criteria

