14.2.2.3 General Notes for Mycological Testing

The study site's local microbiology laboratory will perform identification and *in vitro* susceptibility testing as per their local standards. The Investigator should ensure that fungal isolates obtained from all cultures performed during the study period (and wherever possible, the isolate from the initial positive culture) are sent to the central microbiology laboratory, as described in the laboratory manual. The central microbiology laboratory will repeat the identification and perform *in vitro* susceptibility testing of the isolates as per CLSI M27-A4 and or EUCAST guidelines.^{10,11} Baseline isolated pathogens and subsequent isolates will be subjected to ibrexafungerp susceptibility testing. The central laboratory will include standard of care antifungals in the drug panels to determine resistance patterns.

Further evaluation to identify the potential mechanism of resistance may be performed. Isolates may be maintained in a repository for potential future use, for subjects that provide consent for future use.

Identification of the fungi isolate by local and central laboratory may be performed using acceptable methods such as culture, PCR, matrix-assisted laser desorption/ionization (MALDI-TOF) or others that are approved for such use or are considered acceptable in the state of the art and current guidelines.

Table 11: Fungal Isolates to be Collect for the Study.

Fungal isolate	Definition	When to Send to Central Laboratory
Initial Isolate	The isolate from the culture that resulted in the initial diagnosis of invasive fungal disease will be considered the “initial” isolate. All subjects except those diagnosed solely based on non-culture tests like T2, PCR or serological tests will have an isolate from an initial culture.	End of Study for each subject.
Screening Isolate	Subjects with refractory or resistant fungal disease will have cultures that are positive after the initial positive culture (thereby qualifying the subjects as “refractory or resistant” for study eligibility). This will be referred to as the “Screening” Isolate.	For subjects refractory or resistant to an echinocandin, the isolate should be sent at the time of enrollment per the laboratory manual instructions. Otherwise, screening isolates may be sent at End of Study for each subject.

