Study Isolate	All fungal isolates recovered during study while the subject is receiving ibrexafungerp or during the follow-up window.	End of Study for each subject.

For subjects who are suspected to have a relapse of infection during the study follow-up period, cultures should be collected and other evaluations relevant to the signs and symptoms of infection should be performed before starting non-study antifungal therapy. Results of all mycological tests, including both culture and non-culture based (including negative results), relevant to the fungal infection under treatment should be documented on the eCRF.

Sites should make every attempt to save the initial isolate for the study. However, it is not mandatory to have the initial isolate for enrollment. In the absence of baseline isolates, all post-Baseline pathogens collected in the context of clinical failure and associated with the fungal disease will be stored and shipped to central laboratory for identification of fungal species and susceptibility testing. If the identities of the pathogens differ between the central and local laboratories, the central laboratory results will take precedence over the local results for all study purposes.

Other procedures and assessments will be performed as clinically indicated for the individual subject:

- Suitable samples for fungal culture and isolation (blood/ tissue cultures).
- Follow-up culture samples from non-bloodstream infections are not mandatory but, if obtained, results should be recorded. Histological or cytological findings are regarded as supportive evidence of invasive fungal disease and should be recorded, if available.
- For outcome assessment of fungal blood stream infections, confirmed (two consecutive) negative blood cultures are required.
- All isolates should be identified to species level. All baseline and EOT isolates will be stored and shipped for central retesting. The central laboratory results will be considered definitive.
- Biopsy/biological fluid samples from the infected site for histology and cytology.

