### 7.2.1 Overall Secondary Endpoints

The overall secondary endpoints listed below apply to all eligible fungal diseases:

- The percentage of subjects who achieve Global Response at additional time points as applicable for each disease, disease category and reason for enrollment ([Table 5](#)), as determined by the DRC and by the Investigator
- The percentage of subjects who achieve Clinical Response by pathogen at time points applicable for each disease, disease category and reason for enrollment ([Table 5](#)), as determined by the DRC and the Investigator
- The percentage of subjects who achieve Mycological Response by pathogen at time points applicable for each disease, disease category and reason for enrollment ([Table 5](#)), as determined by the DRC and the Investigator
- The percentage of subjects who achieve Clinical Response by fungal disease, disease category and reason for enrollment at time points applicable for each disease ([Table 5](#)), as determined by the DRC and the Investigator

- The percentage of subjects who achieve Mycological Response by fungal disease, disease category and reason for enrollment at time points applicable for each disease ([Table 5](#)), as determined by the DRC and the Investigator
- The percentage of subjects with a recurrence of the baseline fungal disease at the 25-Day FU for VVC and at the 6-Week FU for all other diseases as determined by the DRC
- ACM at Day 30 (IC and candidemia) and Day 42 for all diseases
- Time to death from any cause
- Describe ibrexafungerp plasma concentrations

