**Mycological Response (Protocol Amendments 2 and 3 aligned with MSG-EORTC outcome response definitions):**

1. Eradication (eradication of the original causative organism cultured or identified by histology/cytology at Baseline)
2. Presumed eradication (missing documentation of the eradication of the original causative organism at Baseline plus resolution of all or some clinical symptoms and physical findings of fungal disease present at Baseline and/or of those that appeared at a subsequent visit)
3. Persistence (persistence of the original causative organism cultured or identified by histology/cytology at Baseline or emergence of a new causative organism)
4. Presumed persistence (missing documentation of the persistence of the original causative organism at Baseline plus no resolution or worsening of any clinical symptoms and physical findings of fungal disease present at Baseline and/or of those that appeared at a subsequent visit)
5. No mycological follow-up results available, for whatever reason (no diagnostic test done at any time point)
6. No mycological evidence at Screening (up to Day 7) (any negative diagnostic test(s) obtained or not done at Baseline [from Screening up to Day 7, inclusive])

Mycological response will be confirmed by the DRC and will include central laboratory results. Reporting of mycological response by PI used different definitions for subjects enrolled under final protocol and subsequent amendments. Complete and partial response were mapped as successful mycological response for subjects under final protocol: Eradication and presumed eradication were mapped as successful mycological response for subjects enrolled under subsequent amendments. The DRC adjudicated mycological responses used the same definition for all subjects as included in the latest amendment.

If relevant mycology findings occur after successful mycological response (proven or presumed eradication), an evaluation will be made as to whether the infection is recurrent (same species as at Baseline) or emergent (different species compared with Baseline). Subjects with recurrent or emergent infection will be classified as mycological failure from the visit onwards where positive cultures were reported, i.e. positive cultures before the FU Visit will be categorized as mycological failure and overall non-successful response on the primary efficacy assessment.

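### Recurrence requires the baseline species to return, but Table 5 admits some subjects with no species identified, and neither document says how to classify their relapse

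*Protocol*

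**What the plan says.** Protocol 18.4.2.2 defines recurrence as a Global Response at EOT followed by return of the baseline disease during follow-up, and adds: "Re-emergence of the fungal disease is required to be with the same species and involving the same site that was initially identified at Baseline". Protocol 7.2 carries the same condition, "with the same fungal species and involving the same site", and anchors the response at TOC for VVC. The SAP does not restate the definition. Its only related rule, in SAP 7.2.3, sorts later mycology findings into two classes: "an evaluation will be made as to whether the infection is recurrent (same species as at Baseline) or emergent (different species compared with Baseline".

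The endpoint in SAP 7.2.1 is "The percentage of subjects with a recurrence of the baseline fungal disease at the 25-Day FU for VVC". Non-VVC subjects are assessed six weeks after treatment ends, and the DRC makes the call. It is listed among endpoints that apply to every eligible disease. SAP 7.2 presents secondary endpoints in the ITT, Myco-ITT and PP populations; SAP 7 makes ITT primary.

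On entry, Protocol Table 5 accepts esophageal candidiasis (EC) on KOH "or fungal stain from biopsy or brushing indicating yeast infection". Invasive candidiasis may rest on histology, or on "Alternative approved diagnostic method such as T2 testing or" beta-D-glucan with a clinical or radiological sign. Protocol Table 11 acknowledges the result: "All subjects except those diagnosed solely based on non-culture tests like T2, PCR or serological tests will have an isolate from an initial culture". Protocol 14.2.2.3 adds that an initial isolate is not a condition of enrollment, and, for follow-up: "Follow-up culture samples from non-bloodstream infections are not mandatory but, if obtained, results should be recorded".

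**The concern.** The endpoint covers all diseases, but its definition needs a piece of baseline information that part of the population is allowed to lack. Take an EC subject enrolled on a stain who responds by EOT and whose symptoms and plaques are back at the 6-Week FU. There is no baseline species to match, so the written rule cannot register the relapse.

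If such subjects are then tabulated as free of recurrence, the rate is too low. The shortfall would be largest where non-culture entry is most common, so rates would not be comparable across diseases. Absence of recurrence is also a component of the treatment-completion endpoint for acute invasive candidiasis and candidemia (Protocol Table 2, SAP Table 7), so missed recurrences could raise that figure.

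The rules are also asymmetric. The investigator's mycological scale allows eradication to be presumed when documentation is missing and symptoms have at least partly resolved (Protocol 18.4.5, SAP 7.2.3). Recurrence has no presumed counterpart.

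**Working it through.** The plan states no recurrence rate, no share of subjects without a species and no calculated sample size, so there is no figure to reproduce. The check is a reading of the text followed by an illustration.

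**Who can lack a species at entry (Protocol Table 5)**

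- EC: KOH or stain.
- OPC and CMC: positive stain from biopsy.
- Invasive candidiasis: histology, or two positive beta-D-glucan tests plus a sign.
- IPA: histology, or galactomannan.
- Other emerging fungi: microscopy showing fungal cells.
- VVC: not affected, because a positive *Candida* culture is required.

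ABPA is a related case: its row in Protocol Table 10 is empty, so no mycology is scheduled against which a later match could be made.

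**Do other rules fill the gap?**

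- DRC discretion (Protocol Table 16 note e, and the text after Table 17) applies where the MSG-EORTC response criteria do not fully fit. Recurrence is a separate definition.
- The unknown or not-evaluable rule (Protocol 18.4.3, SAP 3.3) is triggered by missing data. The EC subject above has follow-up data; what is absent is a baseline species.
- Myco-ITT (SAP 3.2) requires a confirmed pathogen and so removes most affected subjects, but it is supportive.
- No passage states the recurrence denominator.

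**Arithmetic**

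Let u be the share of responders with no baseline species, r_s the recurrence rate in those with one, and r_u the true rate in those without.

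- True rate = (1 − u) × r_s + u × r_u
- Counted rate if they stay in the denominator as non-recurrent = (1 − u) × r_s
- Bias = −u × r_u
- Counted rate if they are left out = r_s; difference from truth = u × (r_s − r_u)

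With equal risk (r_s = r_u), the counted rate when they are kept is:

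| u | True 5% | True 10% | True 20% |
|---|---|---|---|
| 10% | 4.5% | 9% | 18% |
| 20% | 4% | 8% | 16% |
| 30% | 3.5% | 7% | 14% |
| 40% | 3% | 6% | 12% |

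The shortfall runs from 0.5 points (0.10 × 5%) to 8 points (0.40 × 20%). Both u and the true rates are assumptions.

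For scale, Protocol 7.1 reports 11 Global responders among 20 reviewed subjects (11 + 6 + 2 + 1 = 20; 11/20 = 55%). Applied to 220 subjects, that is 121 responders. With a true rate of 10% and u = 20%, 121 × 0.8 × 0.10 = 9.7, about 10 counted events. Clopper-Pearson intervals are 4.0% to 14.7% for 10/121 (kept) and 5.1% to 18.1% for 10/97 (left out).

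The denominator also matters in its own right: 12.1 true events are 10% of 121 responders but 5.5% of 220 treated subjects.

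Exclusion is unbiased only under equal risk. With u = 20% and r_s = 10%, r_u = 5% gives a true 9% against a reported 10%, and r_u = 20% gives a true 12% against a reported 10%.

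**The case against.** A reader might infer that these subjects can never be recorded as recurring and that the reported rate is therefore understated. The documents do not establish either. The DRC determines recurrence, and its Charter, which Protocol 18.4.4 says will hold detailed outcome criteria, is not among the documents. No passage says that an unmatched relapse is tabulated as no recurrence, and if these subjects are left out at equal risk the bias is zero.

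Other points also stand:

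- Entry without culture does not mean no species is ever found. Protocol 14.2.2.2 plans mycological samples at Screening or Baseline for all non-VVC subjects, and 14.2.2.3 accepts PCR for identification. Table 5 accepts distinctive morphology for dimorphic fungi.
- Protocol 14.2.2.3 asks for cultures when relapse is suspected in follow-up. Table 10 schedules mycology at the 6-Week FU for every disease it covers except ABPA. This limits how much weight the non-mandatory follow-up cultures can bear.
- Relapse is visible elsewhere. DRC-assessed Global Response at the 6-Week FU needs no species match.
- It is tempting to say that ABPA recurrence must approach 0%. That goes too far. ABPA entry may rest on *A. fumigatus*-specific IgE or precipitins, and ABPA exacerbation, defined without a species, has its own endpoints.
- The species rule has a purpose: it separates recurrent from emergent infection.

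These points reduce the number affected and the consequences. They do not supply the missing rule: the discretion clause and the unknown category, as worded, do not reach a subject who has follow-up data but no baseline species.

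**Conclusion.** The point holds in conditional form. The recurrence definition cannot be met, as written, by a responder with no species identified at baseline, and neither document gives a fallback or a denominator. If such responders stay in the ITT or PP denominator as non-recurrent, the rate is low by their share times their true risk. That is 4 points at a true 20% with one responder in five affected (20% becomes 16%), and 0.5 to 8 points over the assumed range. The actual size cannot be computed because the share is not given.

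VVC is unaffected, as are subjects whose screening culture or PCR yields a species; Myco-ITT is largely unaffected. This is a descriptive secondary endpoint in an exploratory single-arm study, so the correction is one that should be made rather than one on which the primary result depends.

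**What to change.** In Protocol 18.4.2.2, SAP 7 and 7.2, and the DRC Charter:

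1. Keep same species and same site as *proven recurrence* wherever a baseline species exists.
2. Add *presumed recurrence*, adjudicated by the DRC, for responders with no baseline species whose disease returns at the same site on the type of evidence that qualified them for entry.
3. State the denominator as Global responders at EOT (TOC for VVC).
4. Report proven, proven plus presumed, and not assessable in separate rows.

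The cost is wording and extra table rows; no new procedure is needed. Some presumed recurrences may be new infections, and the stated rate may rise. The separate rows let the reader see how much of the rate depends on the presumed class.
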